| | Days 8 through 12: TAS-102 (35 mg/m ² /dose) orally 2 times daily with the first dose administered in the morning of Day 8 of each cycle and the last dose administered in the evening of Day 12. TAS-102 is to be taken within 1 hour of completion of morning and evening meals. |
| | Days 13 through 28: Rest |
| | Treat subjects on protocol until progression of disease on the study drug or intolerance after pre-specified dose reductions or subject desire to come off treatment |
| | Primary Endpoint: |
| | • The progression free survival (PFS) defined as the duration of time from study entry to time of progression or death or the date of last contact, whichever occurs first. |
| | Secondary Endpoints: |
| Enapoints: | The objective response rate (ORR) by RECIST 1.1 criteria The Clinical Benefit Rate (CR + PR + SD) The time to progression (TTP) Overall survival (OS) The sofatu profile and tolerability in this perpulation |
| | The safety profile and tolerability in this population Compliance with intended treatment |

| Study Design: | Open-label, non-randomized, sequentially enrolling single arm phase II trial |
|------------------------|---|
| Accrual Goal: | 33 subjects |

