3. SELECTION OF SUBJECTS

3.1 Number of Subjects

A total of 33 patients with metastatic or locally advanced unresectable pancreatic adenocarcinoma after progression through first line chemotherapy.

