Relevant visit data should be entered on the CRF and any unused study medication will be accounted for and returned for all subjects participating in the study who receive study drug. Subjects who discontinue following study consent will have relevant information completed and recorded on the CRF. All subjects who discontinue because of adverse events or clinically significant laboratory abnormalities should be followed up until they recover or stabilize, and the subsequent outcome will be recorded. If any subject should die within 30 days of receiving study treatment, the Investigator will inform the UF Health Data Integrity and Safety Committee (DISC).

6.3 Replacement of Subjects

Subjects lost to follow up along with other clinical variables without values are considered as missing data. We are not planning to do missing data imputation. These subjects will not be replaced on the trial unless they were lost to follow-up prior to receiving a single dose of the study drug.

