12.1 Sample Size Determination

This is a pilot phase II single-arm study, with a primary endpoint of progression-free survival (PFS), to evaluate efficacy of TAS-102. Additional objective of the study is to evaluate the feasibility and safety of a regimen of daily TAS-102 administered to subjects with metastatic or unresectable pancreatic adenocarcinoma after progression through or intolerance to first- or second-line chemotherapy. The primary efficacy analysis will be an intent-to-treat comparison of the PFS curve with a reference historical control. From past studies³, the median PFS and/or time to progression (TTP) for subjects with metastatic or unresectable pancreatic adenocarcinoma in the second line of treatment is variable ranging from 6 weeks to 22 weeks. Assuming exponential distributions on PFS on both current study population and the referent population, a sample size of 33 evaluable subjects who will receive the same level of dose will ensure to have at least 80% power to detect an improvement of 3 weeks of median PFS (i.e. from 6 weeks to 9 weeks). The sample size and power derivations were based on one-sample log rank test by Wu $(2015)^{14}$ at one-sided significance level of 0.10. It is assumed that the survival time distributions of both groups (historical and this proposed experiment groups) are approximately the Weibull distribution with a shape parameter of ~ 1.0 . Accounting for about $\sim 10\%$ ineligible/inevaluable subjects, the total number of subjects to be accrued to this cohort will be 37, which is expected to be completed within 24 months. Assuming at least the last evaluable subject derives benefit from the anticipated maximal number of 6 cycles, the length of the entire treatment study will be approximately 30 months.

A subject is considered eligible for toxicity evaluation if they have received at least one dose of TAS-102.

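### Enrolment total conflicts: 33 in the synopsis and section 3.1, but 37 accrued to obtain 33 evaluable in section 12.1

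*Combined protocol and SAP*

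**What the plan says.** Three places in the current text give a number of subjects.

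- Protocol synopsis, table row: "Accrual Goal: | 33 subjects".
- Section 3.1, Number of Subjects: "A total of 33 patients with metastatic or locally advanced unresectable pancreatic adenocarcinoma after progression through first line chemotherapy".
- Section 12.1, Sample Size Determination: the power statement rests on "a sample size of 33 evaluable subjects who will receive the same level of dose". After an allowance of about 10% for ineligible or inevaluable subjects, "the total number of subjects to be accrued to this cohort will be 37".

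Two other statements bear on the point. Section 12.1 sets the analysis: "The primary efficacy analysis will be an intent-to-treat comparison of the PFS curve with a reference historical control". Section 6.3, on subjects lost to follow-up, says "These subjects will not be replaced on the trial unless they were lost to follow-up prior to receiving a single dose" of study drug.

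On timing, the synopsis gives an estimated enrolment period of 30 months. Section 12.1 says of accrual, "which is expected to be completed within 24 months", and uses 30 months for the length of the whole treatment study.

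**The concern.** The synopsis and section 12.1 both speak of accrual and attach different numbers to it. Section 3.1 does not use that word, but it gives 33 as the total under a heading that a reader would take as the enrolment figure. The number that 12.1 reserves for evaluable subjects appears elsewhere as the number to enrol.

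This figure decides when enrolment stops. A site working from the synopsis or 3.1 would close at 33, which uses up the margin that 12.1 planned. A site working from 12.1 would enrol 4 subjects beyond the goal in the synopsis. It would then also be unclear which target the trial's actual accrual should be judged against.

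**Working it through.** **1. The inflation step in 12.1.** Inputs: 33 evaluable and a 10% allowance.

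- 33 / (1 − 0.10) = 36.67, rounded up to 37. This reproduces the plan.
- In reverse, 37 × 0.90 = 33.3 evaluable.
- If 33 were the total enrolled, 33 × 0.90 = 29.7, so 29 to 30 evaluable.
- Gap between the totals: 37 − 33 = 4 subjects, and 4/37 = 10.8%.

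**2. The base figure of 33.** Inputs from 12.1: one-sample log-rank test, exponential PFS, medians 6 weeks (null) and 9 weeks (alternative), one-sided alpha 0.10, power 80%, accrual over 24 months (104 weeks). Assumptions: uniform accrual, and 26 weeks of minimum follow-up, inferred from 30 − 24 = 6 months.

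With λ0 = ln 2/6, λ1 = ln 2/9, accrual a = 104 and follow-up f = 26:

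- p1, the probability of an observed event under the alternative, is 1 − [exp(−λ1 f) − exp(−λ1(a + f))]/(λ1 a) = 0.9832.
- p0, the expected null cumulative hazard under the alternative, is p1 × 9/6 = 1.4747.
- V1, the per-subject variance of expected minus observed events under the alternative, is 2.1404.
- n = (1.2816·√V0 + 0.8416·√V1)² / (p0 − p1)².

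Section 12.1 does not say which null variance V0 was used, so I took two forms.

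- V0 = p0: (1.2816 × √1.4747 + 0.8416 × √2.1404)² / 0.4915² gives n = 32.16, so 33. This reproduces the plan.
- V0 = (p0 + p1)/2: n = 29.10, so 30.

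**3. Power by number analysed.** Formula: Φ{[√n (p0 − p1) − 1.2816·√V0]/√V1}. The simulations used 400,000 trials per n, with O observed and E expected events.

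| Analysed | Formula, V0 = p0 | Formula, averaged V0 | Simulated, (E−O)/√E | Simulated, (E−O)/√((E+O)/2) |
|---|---|---|---|---|
| 29 | .7721 | .7991 | .7916 | .8094 |
| 30 | .7813 | .8077 | .8009 | .8175 |
| 33 | .8069 | .8312 | .8292 | .8437 |
| 37 | .8365 | .8583 | .8615 | .8731 |

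Simulated type I error at 33 is .0832 and .0941 for the two statistics.

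**4. Sensitivity to the follow-up assumption.** For 8 to 52 weeks of minimum follow-up, formula power is 79.8% to 83.2% at 33 and 76.2% to 80.8% at 29 to 30. The low end at 33 is 8 weeks with V0 = p0, where n = 33.31 and power is .7975.

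**5. The enrolment period.** With 130 weeks of accrual (30 months) in place of 104, and 26 weeks of follow-up, n is 32.14 against 32.16. This discrepancy does not affect the sample size.

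**The case against.** **33 may mean treated or eligible patients and 37 registered ones.** Section 4 enters all consented subjects in the trial management system, section 5 numbers everyone who enters screening, and section 6.1 treats those never dosed as screening failures. The 37 expressly includes ineligible subjects, and 3.1 sits under the selection criteria. The reading is possible, but no section states it or ties the 10% to screening failures, and the synopsis still labels 33 as the accrual goal.

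**Intent-to-treat and replacement may make 33 enough.** A dosed subject later lost to follow-up stays in an intent-to-treat analysis, and 6.3 replaces subjects lost before a first dose. For efficacy, 12.1 defines no evaluable set that would remove anyone, so the case of 29 to 30 analysed has no stated exclusion rule behind it. This stands, and it is why I claim no material power loss. It does not remove the conflict. Section 6.3 is silent on subjects found ineligible after enrolment, and if everyone enrolled is analysed, the allowance and the 37 in 12.1 have no stated purpose. One of the passages must change on either reading.

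**The 80% claim at 33 is conditional.** This also stands. It holds with 26 weeks of follow-up, but with 8 weeks and the larger null variance power is 79.8%.

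**Conclusion.** The concern holds. The current text gives two enrolment totals, 33 and 37, and nothing in the documents reconciles them. It is an inconsistency and not a calculation error, since 12.1 agrees with itself and both of its numbers reproduce. The likeliest explanation is that the evaluable number was carried into the synopsis and 3.1 as the enrolment number, though the documents do not prove this.

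The consequence is modest. Within any one column of the power table, going from 33 analysed to 29 or 30 costs between 2.4 points (.8312 − .8077) and 3.8 points (.8292 − .7916), and the resulting power straddles 80%. That loss arises only if about 10% of the 33 are left out of the analysis. These figures rest on the assumed 26 weeks of follow-up and on the two variance forms, while the 33-against-37 conflict needs no assumption. It should be corrected because this number governs when enrolment closes.

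**What to change.** Change the synopsis Accrual Goal and section 3.1 to read: *37 subjects accrued to obtain 33 evaluable*. This matches 12.1 and needs no design change.

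If 33 accrued is the true ceiling, correct 12.1 instead. Remove the 37 and the 10% allowance, and state that the 33 behind the 80% claim are all 33 accrued, analysed by intent-to-treat.

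As a minor item in the same amendment, align the enrolment period (30 months in the synopsis, 24 months in 12.1). The documents do not show which is right.

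The cost is a wording change in two places, or in the sample-size paragraph of 12.1.

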12.2 Analysis of Baseline and Demographic Characteristics

The analysis of demographic characteristics (age, gender, ethnicity) and baseline characteristics, including weight change, performance status, and histologic subtype, will be primarily descriptive due to the small subject numbers. All data will be summarized using descriptive statistics (mean/variance, median/range, frequency/proportion) along with graphical illustration as needed.

12.3 Primary and Secondary Endpoint Efficacy Analysis

The primary endpoint to this study will be to determine progression-free survival following TAS-102 therapy. Kaplan-Meier mean estimates and survival curves of progression-free survival rates will be calculated.

A secondary endpoint of this study will be overall survival/TTP following treatment with TAS-102. Kaplan-Meier estimates and survival curves will be calculated. Other secondary endpoints include response rates, clinical benefit rate (CR + PR + SD), toxicities, reversibility of toxicities, and compliance with intended treatment will also be estimated along with exact 95% binomial confidence intervals.

No multiplicity will be adjusted for the secondary endpoints. All data analysis will be conducted in reproducible fashion and the results will be reported regardless of the statistical significance.

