| Statistical Considerations: | The analysis of demographic characteristics (age, gender, tobacco abuse history and ethnicity) and baseline characteristics, including weight change, performance status, and histologic subtype, will primarily be descriptive. Kaplan-Meier estimates and survival curves for PFS, TTP and overall survival will be calculated. Secondary endpoints include response rates, clinical benefit rate (CR + PR + SD), toxicities and reversibility of toxicities) will also be estimated along with exact 95% binomial confidence intervals |
| Estimated Enrollment Period: | 30 months |
| Estimated Last Subject Enrollment Date: | June 15, 2020 |

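### Section 12.3 summarises PFS with a Kaplan-Meier mean and does not carry over the median hypothesis, reference value, test or alpha set in section 12.1

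*Combined protocol and SAP*

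**What the plan says.** Section 12.3, which covers the primary and secondary efficacy analyses, describes the PFS analysis in one sentence: "Kaplan-Meier mean estimates and survival curves of progression-free survival rates will be calculated". Nothing else in 12.3 concerns PFS. The exact 95% binomial intervals mentioned there belong to the secondary endpoints. The section closes by promising to report results whatever their statistical significance, which presupposes a test, but it names none for PFS.

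The design is in section 12.1. The analysis sentence there reads: "The primary efficacy analysis will be an intent-to-treat comparison of the PFS curve with a reference historical control". The hypothesis is on the median, with "at least 80% power to detect an improvement of 3 weeks of median PFS (i.e. from 6 weeks to 9 weeks" weeks being the stated contrast. On the method, "The sample size and power derivations were based on one-sample log rank test", "at one-sided significance level of 0.10". The distributional basis is given as "Assuming exponential distributions on PFS on both current study population and the referent population". The log-rank sentence concerns the sample size and power. No sentence says that this test will be run on the trial data, and none says that a median will be reported.

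The Statistical Considerations row of the synopsis says: "Kaplan-Meier estimates and survival curves for PFS, TTP and overall survival will be calculated". It does not use the word mean, and it names no test.

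**The concern.** The section that governs the primary analysis asks for a summary on a different scale from the hypothesis and does not repeat the elements needed to judge it.

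- **Scale.** Every PFS benchmark in 12.1 is a median: the historical range of 6 to 22 weeks, the 6-week reference and the 9-week target. For an exponential time the mean exceeds the median by a factor of 1/ln 2, about 1.44. A mean set beside these figures flatters the drug.
- **Definition.** The Kaplan-Meier mean is the area under the curve. If the longest time is censored, the curve does not reach zero and the area is defined only up to a chosen time. The plan states no such time.
- **Decision rule.** The power calculation uses a 6-week reference, but 12.1 also quotes a range up to 22 weeks, and 12.3 fixes neither the reference nor the test and alpha. A reader of 12.3 alone could not reconstruct the primary test.

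**Working it through.** **1. Reproduce the plan's sample size, to confirm which test and alpha belong to the design.**

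Inputs from 12.1: medians 6 and 9 weeks, exponential; one-sided alpha 0.10; power 80%; accrual over 24 months; total length about 30 months, which I read as 6 months of follow-up after the last entry. Uniform accrual is assumed.

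One-sample log-rank formula, with exact variance under the alternative:

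n = (z₀.₉₀·√v₀ + z₀.₈₀·σ)² / (v₀ − v₁)²

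Here v₁ is the event probability, v₀ the expected cumulative null hazard and σ² the variance of observed minus expected events, all under the 9-week median.

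- v₁ = 0.9833, v₀ = 1.4750, σ² = 2.1414
- n = (1.2816 × 1.2145 + 0.8416 × 1.4634)² / 0.4917² = 32.16, rounded up to 33
- Power at n = 33: 80.7% (82.9% by simulation)
- 33 / (1 − 0.10) = 36.7, rounded up to 37

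Both stated figures, 33 evaluable and 37 accrued, reproduce. A two-sided 0.10 test would need 43.1, so the one-sided reading is the one that fits.

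**2. Put the hypothesis on the mean scale.** Exponential mean = median / ln 2.

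| Median PFS (weeks) | Mean PFS (weeks) |
|---|---|
| 6 (reference) | 6 / 0.6931 = 8.66 |
| 9 (target) | 9 / 0.6931 = 12.98 |

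The no-benefit mean lies 9 − 8.66 = 0.34 weeks below the 9-week target. In the other direction, a mean of 9.0 weeks corresponds to a median of 9 × 0.6931 = 6.24 weeks, close to the reference.

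**3. Dependence on a restriction time.** Restricted mean to time τ = (median / ln 2) × (1 − exp(−τ·ln 2 / median)). The plan gives no τ, so the values below are assumptions that show the range.

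| τ (weeks, assumed) | Median 6 | Median 9 |
|---|---|---|
| 24 | 8.12 | 10.94 |
| 26 | 8.23 | 11.23 |
| 52 | 8.63 | 12.75 |
| none | 8.66 | 12.98 |

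**4. What follow-up as planned would do.** Simulation with 33 subjects, a 9-week median, 24-month uniform accrual and 6 months of further follow-up gives an average Kaplan-Meier mean of about 12.9 weeks against a true 13.0. The longest observed time is typically about 47 weeks. With an assumed 20% random dropout the shortfall is at most about 0.3 weeks.

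**The case against.** The strongest reply is that 12.1 and 12.3 should be read together. Section 12.1 commits to an intent-to-treat comparison of the PFS curve with a historical control. The same paragraph gives the only test, alpha, distribution and reference contrast in the plan, and 33 and 37 reproduce under them. On that reading the gap is one of carry-over between sections. This largely stands, and it rules out two stronger inferences.

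- A reader might infer that the PFS result cannot be compared with the 6-to-9-week hypothesis. That does not follow. The sentence in 12.3 also provides the PFS curve, from which the median can be read, and under the exponential assumption a mean converts to a median on multiplying by ln 2.
- A reader might infer that a null result will be declared a success. No section sets a success threshold on a mean. The misreading is possible, and the 0.34-week gap makes it easy, but the plan does not direct it.

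It can also be said that mean is simply a slip for median. The word is attached only to PFS and not to overall survival or TTP, which is compatible with a slip, but the documents do not settle it. Even if it is one, 12.3 still lacks the test, alpha, reference and interval.

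What the reply does not answer is that the only numerical summary specified for the primary endpoint is on the wrong scale for its benchmark, and that the log-rank test is tied to the sample size and never stated as the analysis.

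**Conclusion.** The point holds as a mismatch between sections 12.1 and 12.3. As written, the primary endpoint is summarised by a mean with no stated restriction time, and the median hypothesis, 6-week reference, one-sample log-rank test and one-sided 0.10 level stay in the sample-size section.

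The size of the scale problem is 8.66 versus 12.98 weeks on the mean scale for 6 versus 9 weeks on the median scale. This rests on the plan's own exponential assumption.

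The restriction-time problem is real in principle, but its size depends on follow-up. A reader might infer a two-week distortion from the 24-week row of the table (12.98 to 10.94 weeks). The plan contains no 24-week cut-off: section 7.1 continues imaging until progression, and section 7.5 continues it after other reasons for stopping until progression or new anticancer therapy. Under the timing in 12.1 the shift is about 0.1 to 0.3 weeks.

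The design, sample size and data collection are not in question.

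**What to change.** In section 12.3:

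1. Replace the Kaplan-Meier mean with the Kaplan-Meier median PFS and its confidence interval, stating the level. A two-sided 80% interval would correspond to the one-sided 0.10 test, since 1 − 2 × 0.10 = 0.80; the choice of level is the sponsor's.
2. State that the primary analysis is the one-sample log-rank test against an exponential reference with median 6 weeks, at one-sided 0.10, in the intent-to-treat set.
3. If a mean is kept, report it as a restricted mean to a time fixed in advance.

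The synopsis does not mention a mean, so it needs at most a matching addition.

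The cost is an amendment of wording. No new data are needed, and 33 evaluable and 37 accrued stay as they are. The change should be made before the PFS data are analysed.

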13 DATA AND SAFETY MONITORING

13.1 Data Integrity and Safety Committee

This protocol will be reviewed and monitored by the University of Florida Health Cancer Center Data Integrity and Safety Committee (UFHCC DISC) in accordance with their policies and procedures. They will review and monitor study progress, toxicity, safety and other data from this trial. Questions about subject safety or protocol performance will be addressed with the sponsor-investigator, statistician and study team members. Should any major concerns arise, the DISC will offer recommendations regarding whether or not to suspend the trial.

UFHCC DISC data and safety monitoring activities include:

- Review of clinical trial conducted for progress and safety
- Review of all adverse events requiring expedited reporting as defined in the protocol
- Review of reports generated by data quality control review process
- Notification of the sponsor-investigator of recommended action
- Notification of sites coordinated by the UFHCC of adverse events requiring expedited reporting and subsequent committee recommendations for study modifications

In compliance with the UFHCC data and safety monitoring plan, the PI will provide a Data Integrity and Safety Committee Report to DISC at the predetermined timelines for the level of risk category assigned during the initial SRMC (Scientific Review and Monitoring Committee) review, which occurs prior to initial IRB approval.

UFHCC investigator-initiated protocols will be classified into one of the following categories of risk:

- Level 1 Low risk non-therapeutic interventional trials.
- Level 2 Moderate risk therapeutic (i.e., drug, biologic, or device) trials using FDA approved or commercially available compounds or interventions.
- Level 3 High risk therapeutic trials (i.e., investigator-sponsored INDs, Phase I trials, studies requiring biosafety approval, or other areas that may be designated by NIH as high risk).
- Level 4 Complex trials involving very high risk to subjects and a high-level complexity (i.e., first in human or gene transfer studies).

13.2 Data Monitoring

UFHCC (University of Florida Health Cancer Center) Quality Assurance team and/or project management officers will perform remote monitoring and may make monitoring visits to the trial sites periodically during the trial to determine if sites are complying with the protocol. Source documents will be reviewed for completion and validated against with data submitted electronically via the Electronic Data Capture. The site investigator/institution guarantee access to source documents by UFHCC or its designee and appropriate regulatory agencies. As part of the responsibilities assumed by conducting the study, the Principal Investigator (PI) agrees to

maintain and have available for monitoring adequate case records (accurate source documents and CRFs) for the subjects treated under this protocol.

The trial site may also be subject to quality assurance audit by any collaborating sponsors or their designee as well as inspection by appropriate regulatory agencies.

It is important for the site investigator and their relevant personnel to be available during the monitoring visits and possible audits and for sufficient time to be devoted to the process.

